### Tumor Biopsy Processing

Prior to initiation of therapy, tumor samples will be collected by direct or ultrasound-guided core biopsy from accessible tumor tissue. A maximum of 6 core tissue samples will be obtained from each patient. Core biopsy is preferred and FNAs are only to be done when core biopsy is not safe (such as with lung lesions). There are 4 parts to the procedure: preparation, slide creation, dry protocol, and RNA later protocol. **Biopsies must be flash frozen within minutes of biopsy collection, and immediately stored at -70C or below. Biopsies may be batched and shipped at the end of this study to [name] laboratory as detailed in this protocol. DO NOT ship biopsies out on Thursday or Friday to prevent weekend arrival; shipment should occur the following Monday. All samples, blood and biopsies MUST BE OVERNIGHT EXPRESSED to ensure next day delivery. When preparing for shipment, fill an insulated styrofoam box with DRY ICE (NOT ICE), enough to fill at least 3/4 of the box. This will ensure that plenty of dry ice remains during the duration of the delivery process to protect the quality of the specimens. Fill half the box with DRY ICE, place the specimens in the middle, and fill up to top with DRY ICE.**

#### a. CORE BIOPSY PROTOCOL

##### i. Preparation:

CONFIDENTIAL

This document is confidential. Do not disclose or use except as authorized.

1. Prepare a 50:50 mixture of dry ice and isopropanol mixture in a styrofoam bucket to a depth of 1 inch. A liquid nitrogen bath is also acceptable.
2. Label 5 cryovials with Patient ID, Cycle/ Day, Specimen Type (biopsy, location), and Date of collection.
3. Fill one of the vials with 1mL RNAlater and add RNAlater designation on the tube.

ii. Slide creation:

1. The first biopsy passage should be used for the creation of an H&E or cryoslide which an onsite pathologist will use to confirm the biopsy is tumor tissue.
  - a. If it is not possible to obtain an onsite pathologist, please create an H&E slide and send to [name] laboratory for analysis
  - b. After the pathologist's confirmation, keep and store slides at room temperature and send to [name] laboratory.

iii. Dry protocol:

1. During each of the subsequent passes, transfer each biopsy to an enclosed empty 1.8mL cryovial (Use sterile techniques)
2. Flash freeze each vial immediately by adding the cryovial to the 50:50 mixture in the bucket or in the liquid nitrogen.

iv. RNAlater protocol:

1. On the last passage, add a core biopsy to the cryovial filled with RNAlater and flash freeze by immersing the tube in the 50:50 mixture or liquid nitrogen.
  - a. NOTE: **RNAlater is NOT sterile and needle dipped in this solution should not be reused on the patient**
2. Samples will be stored at or below -70C until shipped to [name] via overnight express in DRY ICE. ADD ENOUGH DRY ICE TO FILL AT LEAST  $\frac{3}{4}$  OF THE INSULATED SHIPPING BOX. Biopsies may be batched and shipped at the end of this study to [name] laboratory. Avoid shipping on Thursdays and Fridays to prevent weekend arrival. Store in -70C or below until following Monday to ship for Tuesday arrival.

**b. FNA PROTOCOL**

There are 3 steps to this protocol: preparation, slide creation, and saline protocol.

i. Preparation

1. Prepare a 50:50 mixture of dry ice and isopropanol mixture in a Styrofoam bucket to a depth of 1 inch. A liquid nitrogen bath is also acceptable.

CONFIDENTIAL

This document is confidential. Do not disclose or use except as authorized.

2. Label 5 cryovials with patient identification, date of collection, Cycle/Day, and specimen type (biopsy location.)
3. Add 1mL of saline to each tube.

ii. Slide Creation

1. Perform the first FNA biopsy pass
2. Create an H&E slide or Cryoslide
3. Have an onsite pathologist confirm the sample is of tumor.
  - a. If an onsite pathologist is not available, please send the slides to Hopkins for analysis
  - b. Keep the slides at room temperature

iii. Saline protocol:

1. Transfer subsequent FNA aspirate to separate cryovials filled with saline.
  - a. Inject and swish the cells into the saline
  2. Flash freeze the cells immediately by immersing cryovials to the 50:50 mixture in the bucket.
  3. Samples are to be stored at -70C.
  4. **When shipped, the samples should be shipped overnight express in enough DRY ICE to fill at least  $\frac{3}{4}$  of the box.**

#### 8.3.1.1 Methylation analysis

Genome-wide methylation analysis will be performed using the Infinium Illumina based assay that allows methylation analysis of >450,000 CpG sites covering greater than 14,000 genes. Beta values indicating methylated CpG islands will be isolated. Pre- and post-treatment biopsies will be compared to determine genes that demethylated following treatment. Canonical tumor suppressor genes will be closely scrutinized for CpG island methylation. These results will then be correlated with expression values.

Methylation patterns in the promoter regions of selected tumor suppressor genes will be determined using quantitative real time nested Methylation Specific PCR (MSP). This technology is ideally suited for increasing the throughput of PCR analysis and gaining a level of quantification not possible with the standard MSP analysis. DNA will be isolated from blood, and tumor biopsies and treated with sodium bisulfite under denaturing conditions (123). Bisulfite modified DNA from each post treatment specimen will be analyzed for changes in DNA methylation at specific gene promoters (to include p16, SFRP1, IGFBP3, TFPI2, RASSF1A, and mlh1). PCR primers for these have been described and are in frequent use in the [name] lab.

For each gene, separate PCR reactions will be performed with methylated-specific primers and unmethylated specific primers (as used in conventional gel based MSP analysis). Each reaction will be run in triplicate. A separate PCR reaction

CONFIDENTIAL

This document is confidential. Do not disclose or use except as authorized.

will utilize primers specific for the unmethylated promoter region of the beta-actin gene, a gene necessary for normal cell structure and function, which has never been observed to be methylated in any cancer. Real-time curves for the MSP reaction will be compared to the unmethylated reaction and to the beta-actin control. Mixing experiments utilizing DNA from cell lines methylated at a given locus and a completely unmethylated DNA source (normal DNA) will be performed to determine accuracy of quantification. Assays will be performed on the Bio-Rad I-cycle. Two methods of detection will be compared: non-specific quantification of PCR products using Syber Green, and specific detection using molecular beacons. A ratio of the inverse of the cycle threshold for the methylated gene of interest over the inverse of the cycle threshold for beta-actin will be calculated. This 'methylation index' will be compared pre- and post-treatment.

If changes in methylation pattern are observed by MSP, this result will be further validated by bisulfite sequencing of selected genes

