Methylation-specific PCR (MSP) will be used to detect the presence of methylated alleles for specific genes described below. Genes found to be methylated in pre-treatment specimens will be monitored for post-treatment changes in methylation using MSP. Methylation analysis may then be performed by using a nested MSP approach. The nested MSP approach has a sensitivity of 1 in 50,000 methylated allele to determine the genes that are methylated amongst the panel for each patient. A non-nested real-time MSP approach will then be used to follow the biologic response across various time points in the study for the genes of interest. This strategy of nested MSP followed by non-nested MSP has been validated in the ongoing study in the MDS/AML patients using bone marrow specimens as a

CONFIDENTIAL

This document is confidential. Do not disclose or use except as authorized.

useful monitoring tool for biologic response.

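### The candidate-gene 'methylation index' is a ratio of cycle thresholds, so it does not normalise for DNA input and it compresses real changes in methylation

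*Combined protocol and SAP*

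**What the plan says.** Section 8.3.1.1 runs methylated and unmethylated primer reactions for each candidate gene, plus a reference reaction that "will utilize primers specific for the unmethylated promoter region of the beta-actin gene". From the Ct values it forms "A ratio of the inverse of the cycle threshold for the methylated gene of interest over the inverse of the cycle threshold for beta-actin". It then states: "This 'methylation index' will be compared pre- and post-treatment".

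The same section lists these quality steps:
- Replication: "Each reaction will be run in triplicate".
- The real-time curves are compared with the unmethylated reaction and with beta-actin.
- Mixtures of methylated and unmethylated DNA "will be performed to determine accuracy of quantification".
- A conditional check: "If changes in methylation pattern are observed by MSP, this result will be further validated by bisulfite sequencing of selected genes".

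Neither the introduction to section 8 nor section 8.3.1.1 states a fixed DNA input, a standard curve, or a conversion to a Ct difference.

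The two places also differ on the assay. In section 8.3.1.1, promoter methylation "will be determined using quantitative real time nested Methylation Specific PCR (MSP". In the introduction to section 8, nested MSP identifies the methylated genes, and "A non-nested real-time MSP approach will then be used to follow the biologic response across various time points".

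**The concern.** The inverse of one Ct over the inverse of another is simply Ct(actin)/Ct(gene). Each cycle is about one doubling, so Ct behaves as a constant minus log2 of the template. If one sample contains less DNA, both Cts rise by about the same number of cycles. Their difference is unchanged; their ratio is not. The beta-actin reaction therefore does not do, in this formula, what a reference reaction is normally run to do.

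At stake is the gene-level pre/post reading by PCR in tumour and plasma. A real loss of methylation can look far smaller than it is, and a difference in DNA amount between the paired samples can mask it or change its sign. Section 8 sends patients with evidence of a methylation change on to re-expression studies, so a change missed here could also be missed there.

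**Working it through.** The plan gives no numerical value for the index, so there is no figure to reproduce. The definition comes from section 8.3.1.1. All Ct values and efficiencies below are assumptions. A 10% loss is used as a reference size because section 14.1 uses 10% demethylation in its criterion for moving to phase II; that criterion is for the LINE assay, not for this index.

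**Model.** Let A = Ct(actin), G = Ct(gene), and let both reactions have efficiency E. Then Ct = K - log(template)/log(1+E).
- Index = (1/G)/(1/A) = A/G.
- Input changed by fold f: both Cts shift by d = -log(f)/log(1+E), so the index becomes (A+d)/(G+d). This equals A/G only if d = 0 or A = G.
- True loss r of methylated template: G rises by δ = -log(1-r)/log(1+E). At E = 1, δ is 0.152 for r = 10% and 1 for r = 50%.

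**Compression at equal input, 25/30.** Baseline 25/30 = 0.8333. A 50% loss gives 25/31 = 0.8065, a change of -3.2%. A 10% loss gives 25/30.152 = 0.8291, or -0.50%. A 90% loss (δ = 3.322) gives -10.0%.

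**Input drift, 25/30, no true change.** Half the DNA gives 26/31 = 0.8387; one tenth gives 0.8499; double gives 24/29 = 0.8276.

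**Both together, for several assumed Ct pairs (E = 1).** Changes are relative to each pair's baseline index.

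| Actin/gene Ct | Half input, no true change | True 10% loss, equal input | True 10% loss, half input |
|---|---|---|---|
| 25/30 | +0.65% | -0.50% | 26/31.152: +0.15% |
| 22/30 | +1.17% | -0.50% | 23/31.152: +0.68% |
| 22/25 | +0.52% | -0.60% | 23/26.152: -0.06% |
| 30/33 | +0.29% | -0.46% | 31/34.152: -0.15% |
| 30/27 | -0.36% | -0.56% | 31/28.152: -0.90% |

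The sign reverses at 25/30 and 22/30. At 22/25 the loss is almost cancelled but keeps its sign. At 30/27, where the gene Ct is below the actin Ct, lower input exaggerates the loss.

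**Reduction in input that exactly cancels a true loss.** Setting (A+d)/(G+δ+d) = A/G gives d* = Aδ/(G-A), a fold of 2^d* at E = 1.

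| Actin/gene Ct | 10% loss | 50% loss |
|---|---|---|
| 20/35 | 1.15-fold | 2.52-fold |
| 22/32 | 1.26-fold | 4.59-fold |
| 25/30 | 2^0.760 = 1.69-fold | 2^5 = 32-fold |
| 22/25 | 2^1.115 = 2.17-fold | 2^7.333 = 161-fold |
| 28/30 | 4.37-fold | 16,384-fold |

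For the pairs re-run at E = 0.9 (all those in this table except 22/25) the cancelling folds are the same.

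**Comparator.** 2^-(G-A) at 25/30 is 2^-5 = 0.03125 at every input when the efficiencies are equal, and losses of 10% and 50% read as relative values of 0.90 and 0.50. If the efficiencies differ, this is not exact. With 90% for the gene and 100% for actin, 8-fold less DNA raises the gene Ct by log(8)/log(1.9) = 3.24 and the actin Ct by 3. The uncorrected value is then multiplied by 2^-0.24 = 0.85, about 15% low with no true change.

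**The case against.** The strongest reply is that the drift needs unequal input, and the documents do not say that input is unequal. If the laboratory loads equal DNA, most of the drift goes. That stands, but the plan states no such step and the compression remains.

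The quality steps also count for something. The unmethylated reaction is a same-locus comparison, but no rule brings it into the index. Triplicates reduce random error only. The mixing experiments are described as varying the methylated share, not total DNA. Bisulfite sequencing can expose a false change, but it follows only a change already seen by MSP and so cannot recover a hidden one.

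Several stronger readings are tempting and are not supported:
- A reader might infer that a two-fold input difference always outweighs a 10% loss. At 22/25 and 30/33 it does not, and cancelling a halving usually needs a very large difference.
- A reader might infer that the phase I methylation result, the move to phase II, or the phase II marker work rests on this index. In section 14.1, the phase I analysis names LINE-1 and gene expression, the criterion for moving to phase II is a LINE assay, and the marker analyses use global methylation and expression. Section 14 does not mention the index.
- A reader might take it as the only gene-level measure in tumour. Section 8.3.1.1 also plans a genome-wide array comparison of paired biopsies.
- A reader might attribute the absence of a clear demethylation pattern at cycle 1 day 8 (section 8.3.1) to this formula. The documents do not say which measure lay behind that statement.

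**Conclusion.** The concern holds for the candidate-gene MSP correlative in tumour and plasma, and for nothing beyond it. As defined, the index does not normalise for DNA input unless the two Cts are equal, and it strongly compresses true changes. The failure to cancel input is algebra. Its size and direction rest on the assumed Ct pair, on the two reactions having similar efficiency, and on how far DNA amount differs between paired samples, none of which the documents give. It should be corrected because a laboratory following the stated rule could report a muted, absent or wrong-signed change. It does not threaten PFS, dose selection or the decision to start phase II. The nested versus non-nested difference is a separate inconsistency about which Ct values enter the index.

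**What to change.** In section 8.3.1.1, replace the index sentence with: relative methylation = 2^-(Ct gene - Ct beta-actin), compared pre- and post-treatment on the log2 (delta-Ct) scale. State that equal efficiency of the two reactions is assumed, and correct for efficiency where a dilution standard provides it. The planned mixing experiments should not be relied on for this unless they also vary total DNA.

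The formula change costs only rewording. It uses the same triplicate Ct values, and samples already analysed can be recomputed if those values were kept. Efficiency correction needs a dilution standard, which would be extra laboratory work if none exists.

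Separately, reconcile section 8.3.1.1 with the introduction to section 8 and state whether nested or non-nested real-time MSP supplies the Ct values for the comparison. This is an assay decision, not just a wording change.

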#### 8.3.1.2 Expression analysis

The goal of DNA methyltransferase inhibition is reversal of transcriptional inhibition due to repressive chromatin conformation related to hypermethylation and changes in histone tails along with changes in miRNA. Given the heterogeneity of metastatic colorectal cancer the selection of specific genes to be studied across patient samples is challenging. Evaluation of expression of genes that become demethylated post-treatment will be performed using quantitative real-time PCR, whenever possible. Gene re-expression will be studied also using genome wide strategies using quantitative PCR using the Ampliflour if additional funds are available. Universal amplification and detection system (Intergen). This system has the advantage of the use of multiple fluorophores for each gene (up to four fluorophores can currently be analyzed). RT-PCR used semi-quantitatively will be combined with real-time quantification using the ABI 7700 system within the Johns Hopkins Oncology Center. Beta-actin will be used as a control. Expression will be reported as a ratio of gene specific to control gene expression levels.

#### 8.3.2 Research Blood

Blood samples for methylation analysis will be collected from all participants into the enclosed purple top tubes (10 mL EDTA BD Vacutainer cell preparation tubes, Becton Dickinson, Franklin Lakes, NJ). These tubes are designed to separate plasma and mononuclear cells from whole blood. For each collection day, total of 50 mL of blood will be drawn from the patient (5 tubes of 10 mL each). Each purple tube holds approximately 10 of blood, yielding close to 5ml of plasma.

Blood tubes must be kept in ice, and processed within 30 minutes of collection. If collected at the Johns Hopkins Hospital, the blood samples will be processed in [name] laboratory. For other participating sites, blood must be kept on ice, processed within 30 minutes, and the plasmas and WBC collected must be stored at or below -70C

CONFIDENTIAL

This document is confidential. Do not disclose or use except as authorized.

until they can be shipped to [name] laboratory. Overnight express shipping and use of adequate amount of dry ice will be practiced to preserve the quality of specimen in the shipping process. All collected specimens will be stored at or below -70C in [name] laboratory.

**Processing of Blood: (For Plasma and White blood cells)**

1. Take 1 empty 15 mL conical tube for each K2-EDTA tube collected
2. First add 3 mL of Ficoll-Paque PLUS buffer to each conical tube.  
**(NOTE: Ficoll-Paque PLUS buffer MUST BE KEPT AT 4°C and out of light for storage.)**
3. Using one conical tube for each purple top blood tube, Carefully layer the blood on to Ficoll-Paque PLUS buffer conical tubes by tilting the conical tube at an angle close to horizontal and letting the blood from the purple-top tube run very slowly down the side of the conical tube.  
**THIS IS IMPORTANT.** If done correctly, the blood should sit right on top of the buffer as shown below **(Figure A)**. Repeat this step for each of the tubes.
4. Next, centrifuge tubes for 10 minutes at 3000 rpm at 4°C. Be sure that the centrifuge is balanced. The layers will now separate as shown below **(Figure B)**.
5. Carefully pipet the plasma layer (the clear yellow layer on top) from each conical tube into a new 15 mL conical tube (1 tube for each).  
**Pay careful attention to not draw from the white buffy coat (the second layer below plasma in Figure B).** To ensure this, stop pipetting plasma at a level 3.5 mL above the RBC layer (Red layer at the bottom). For example, if the top of the RBC is at 3mL, then pipet plasma out down to 6.5 mL and stop.
6. Pipet the buffy coat (WBCs) from each conical tube pooling them into a single new 15 mL conical tube.  
**NOTE:** Gently navigate your pipette tip to collect clumps of WBC around the buffy coat. Be careful not to draw the Ficoll-Buffer sitting below the white buffy coat (the third layer).
7. Once plasma and the white buffy coats are collected from each conical tube you should have, depending on the patient sample, 5 conical tubes filled with 4-5 mL plasma each and one, conical tube filled with 2-4 mL WBCs. You may now discard the conical tubes filled with ficoll and RBCs.
8. Take the single conical tube filled with WBCs and add an equal volume of 1x PBS to the volume of WBCs present, mix by inverting 5 times.
9. Take the single tube with pooled WBCs from step 11 and the 5 tubes with plasma from step 8. Spin all five sample tubes in the centrifuge for 5 minutes at 1500 rpm at 4°C. Be sure that the centrifuge is balanced.
10. After centrifugation you may have a small white pellet at the bottom of each of the plasma tubes (5 tubes) and you will have a larger white pellet in the single WBC tube.  
**Be careful not to disturb the pellets in the plasma tubes or the WBC tubes (Although you will not be collecting the pellets from the 4 tubes with plasma you do not want them to contaminate the plasma)**
11. Take the plasma from the 5 conical plasma tubes. Into 6 Eppendorf (1.5 mL) tubes Add 0.5 mL plasma.  
**Do not disturb any pellet that may have formed.**
12. Add the remaining plasma in 1.0 mL aliquots into additional 1.5 mL Eppendorf tubes (between 12 and 16 tubes).  
**Do not disturb any pellet that may have formed.**

CONFIDENTIAL

This document is confidential. Do not disclose or use except as authorized.

13. Now take the conical tube with the WBCs. There should be a white pellet at the bottom **You want this pellet.**
14. **Being careful not to disturb the pellet** Remove by pipetting (**Do not decant**) and discard any liquid from the conical tube (**leave a little liquid ~200 uL behind to make sure the pellet is not disturbed.**)
15. Add 3 mL 1x PBS to the pellet and mix by flicking the tube gently to re-suspend the cells. (**If the cells do not re-suspend by flicking the tube you may carefully pipet the cells up and down to re-suspend them in the PBS**)
16. Once the cells have been re-suspended add 6 aliquots of 0.5 mL of the WBCs in step 18 into 1.5 mL Eppendorf tubes.
17. When finished you should have 6 tubes with 0.5 mL of plasma from step 14; 16-20 tubes with 1.0 mL of plasma from step 15; and 6 tubes with 0.5 mL of WBCs from step 19.
18. Label samples as **PLASMA** OR **WBC**, as applicable, including study number (J1369), unique patient ID (assigned by the consortium), date of collection, and time point in treatment cycle.
19. Freeze plasma and WBC samples in their Eppendorf tubes at or below -70°C until shipment or transfer to [name] Laboratory.

Figure A :

[figure not shown]
[figure not shown]

Figure B:

**CRITICAL POINT:** At time of shipping, fill an insulated styrofoam box with **DRY ICE (NOT ICE)**, enough to fill at least  $\frac{3}{4}$  of the box. This will ensure that plenty of dry ice remains during the duration of the delivery process to protect the quality of the specimens. Fill half the box with **DRY ICE**, place the specimens in the middle, and fill up to top with **DRY ICE**.

CONFIDENTIAL

This document is confidential. Do not disclose or use except as authorized.

- a. Shipping of processed Plasma/WBC can be bundled and sent at the end of the trial. They must be sent via overnight express. Please avoid shipping out on Fridays to prevent arrival of items over the weekend.
- b. Shipping of the biopsies may be sent to [name] laboratory as a batched collection as long as they were prepared and stored according to the instructions outlined above (**must be stored at or below -70C until shipment**). **To avoid weekend arrivals, biopsies must not be shipped out on a Thursday or Friday.**

All tubes must be clearly labeled with the unique patient ID (assigned by the consortium), Cycle and Day, specimen type (Plasma, WBC, or biopsy) and Date of collection.

During the course of the study, blood and tumor biopsies will be shipped from the centers to the coordinating center lab at Johns Hopkins University School of Medicine. After conclusion of the study, samples will be sent for analysis to [name] laboratory at the Yale School of Medicine.

